## PROTOCOL REVISION HISTORY

| Version # | Summary of Changes | Version Date |
|-----------|--------------------|--------------|
|           |                    |              |
|           |                    |              |
|           |                    |              |
|           |                    |              |
|           |                    |              |

**No table of figures entries found.**

## ABBREVIATIONS & DEFINITIONS

| Term                      | Abbreviation | Definition  |
|---------------------------|--------------|---|
| Overall Survival          | OS           | The length of time from either the date of diagnosis or the start of treatment for a disease, that patients diagnosed with the disease are still alive.           |
| Progression-Free Survival | PFS          | The length of time during and after the treatment of a disease that a patient lives with the disease but it does not get worse.                                   |
| Time to Progression       | TPP          | The length of time from the date of diagnosis or the start of treatment for a disease until the disease starts to get worse or spread to other parts of the body. |

**Reference:** National Cancer Institute (NCI) Dictionary of Cancer Terms

[figure not shown]
<http://www.cancer.gov/dictionary>

## PROTOCOL SYNOPSIS

|                                    |   |
|------------------------------------|---|
| Protocol Title              | Long-term Follow-Up and/or Continued Thalidomide (THALOMID®) Maintenance Therapy for Patients Enrolled on Clinical Trial 20030165   |
| Targeted Patient Population | Patients enrolled on Clinical Trial 20030165.   |
| Study Design                | 
The study is designed to provide long-term follow-up and/or to offer continued maintenance thalidomide (THALOMID®) therapy to those patients enrolled in 20030165.
 
Group A: Patients who achieved CR in 20030165 and continue to receive maintenance Thalidomide.
 
Group B: Patients who achieved CR in 20030165, but are not receiving maintenance Thalidomide.
 
Group C: All other patients enrolled in 20030165 who expired or experienced disease progression.
 |
| Treatment Schema            | Thalidomide (THALOMID®) will be administered as per standard of care guidelines to Group A; in compliance with REMS™ program requirements.  |
| Study Duration              | 
Patients in Group A, B and C will be followed until withdrawal of consent, or death.
 
Note: All other patients in Group C who expired on 20030165 will also be included in all analyses.
  |
| Follow-up Required          | All patients will be followed annually by telephone or in-person visit(s), until death or withdrawal.   |
| Objectives                  | 
Primary Objective: To provide long-term follow-up and/or offer continued maintenance thalidomide (THALOMID®) to patients enrolled in 20030165 .
 
Secondary Objective: To continue to evaluate objectives specified for 20030165 (please refer to 20030165 for details).
  |
| Expected Number of Patients | 
Group A: 2
 
Group B: 12
 
Group C: 8
   |
| Expected Number of Centers  | 1-Sylvester Comprehensive Cancer Center (SCCC)
Note: SCCC is inclusive of the constituent satellite sites.  |

|  |  |
|--|--|
| Expected Duration of the Protocol | At least 5 years.  |
| Inclusion Criteria                | 

1. Enrolled on the 20030165 clinical trial.

2. Ability to understand and willingness to sign a written informed consent document.

  |
| Exclusion Criteria                | 

1. Patients who were discontinued from 20030165 for any reason prior to the completion of protocol-specified treatment (e.g. withdrawal of consent).

2. Uncontrolled, intercurrent serious illness including but not limited to ongoing or active infection, symptomatic congestive heart failure, unstable angina pectoris, and/or cardiac arrhythmia.

3. Psychiatric illness/condition likely in the judgment of the Principal Investigator (PI) to limit compliance with clinical study requirements.

 |

## PROTOCOL SCHEMA

## 1.0 BACKGROUND

### 1.1 Study Disease

Mantle cell lymphoma (MCL), a subtype of non-Hodgkin's lymphoma (NHL) that represents a distinct disease entity. The term MCL was proposed in 1992 to unify previously defined subtypes of NHL, such as diffuse poorly differentiated lymphocytic lymphoma, intermediate differentiated lymphocytic lymphoma, centrocytic lymphoma, and diffuse small cleaved cell lymphoma, into a single disease entity (1). According to the International Lymphoma Study Group (ILSG), MCL represents 6% of all NHLs (2). MCL is derived from a subset of naive pre-germinal center cells, and may present with two cytological variants: typical (lymphocytic) or blastic (3-4). In addition, there are three possible patterns of involvement: mantle-zone, nodular or diffuse (4). It has been suggested that the treatment response and survival of the diffuse and nodular patterns are worse than those involving the mantle cell zone. Majlis et al reported 3-year survival rates for mantle-zone, nodular, and diffuse type of 100%, 50%, and 55% respectively (5). The monoclonal B-cells express CD19, CD20, CD22, HLA-DR, CD5, surface IgM and, in most cases, surface IgD. They are negative for CD23 and CD10 (CALLA) antigens (6).

The characteristic cytogenetic abnormality in MCL is the t(11;14) (q13;q32) translocation. Band 11q23 includes the BCL-1 locus, which is the site of the PRAD1 (CCND1) gene encoding for cyclin D1. This rearrangement results in translocation of the BCL-1 locus to the immunoglobulin heavy chain gene enhancer region located at 14q32, causing cyclin D1 over-expression. Cyclin D1 interacts with cyclin dependent kinases 4 and 6 to facilitate the progression of cell through G1 into S phase of proliferation (7).

MCL is one of the worst types of NHL since it incorporates some of the undesirable features of both low-grade and high-grade lymphomas, namely incurability and rapid course respectively (7). Most of the patients present with advanced stage, high international prognostic index (IPI), and extranodal involvement. The incidence of Stage III and IV varies between 75 to 90% of the patients (2, 4, 6-8). In addition, there is a high incidence of extranodal involvement, the most common sites being bone marrow (61-79%), spleen (31-60%), liver (13-30%), peripheral blood (12-30%), and gastrointestinal tract (18-20%) (6-9). Central nervous system (CNS) involvement occurs in about 4% of the patients and is associated with poor prognosis (10).

The long-term survival for patients with MCL is generally poor, with only about 27% of the patients surviving 5 years after diagnosis and 11% of the patients being disease-free after 5 years. In addition, the ILSG found no 5-year survivors with IPI index 4/5, placing MCL among the lymphomas with worse overall prognosis (2). Despite response rates of 50% to 70% to different regimens, all patients eventually develop disease progression after chemotherapy, with the mean survival around 3 years (11).

### 1.2 Study Agent

Patients in Group A will receive daily oral thalidomide (THALOMID®) as per standard of care and THALOMID® REMS™ guidelines (formerly known as *S.T.E.P.S.*).

### 1.3 Rationale

Several studies using combination chemotherapy with or without anthracyclines (CHOP or COP) showed responses between 56% and 90%, with CR rates ranging from 9% to 58%. However, relapse-free survival was relatively short with average of 15 to 20 months. Median survival in most studies ranged from 28 to 52 months (12). Therapy with fludarabine alone or in combination with other chemotherapeutic agents has been tested in small trials. In a recent study, Cohen et al obtained response rates of 66% (30% CR) in a study involving 30 patients treated with fludarabine and cyclophosphamide. The overall survival for patients receiving this combination as first line therapy has not been reached at 43 months, although failure-free survival was 28 months (13). In another study involving 29 patients, Zinzani et al achieved a 63% overall response (28% CR) using fludarabine alone or in combination with idarubicin (14). Rituximab has also been tested in MCL. Igarashi et al treated 21 patients with refractory or relapsed MCL, achieving a 31% response rate (no CR observed) (15). Howard et al obtained a 96% response rate (48% CR) in 25 patients with MCL, using a combination of CHOP and rituximab. 25 patients were evaluated for molecular remission, which was seen in 9 of them. However, the achievement of CR or molecular remission did not translate into a prolonged progression-free survival, which was 16.6 months (16). Khouri et al, treated patients with Hyper-CVAD, an aggressive regimen alternating cycles of cyclophosphamide, doxorubicin, vincristine, and dexamethasone and high-dose methotrexate and cytarabine. This regimen induced a 93% response rate with 82% CR. This therapy was followed by stem cell transplantation and 93% of previously untreated patients were alive at 3 years post-transplant, 73% of them disease-free (19).

Although encouraging results have been reported for stem cell transplant (SCT), its role in the treatment of patients with MCL remains unknown. Overall 3-year survival for MCL patients previously treated ranges between 24% to 59%, with one study, performed by Milpied et al, reporting 80% overall survival at 4 years (20- 22). Event-free survival (EFS) or progression-free survival (PFS) at three years however, ranges between 17% to 48% (19, 22). Stewart et al, reported a 23% overall survival for SCT in MCL patients in first remission. EFS/PFS however, was only 8% (23). There have been few small studies on the use of allogeneic SCT in MCL. The reported overall survival is 55% to 62% at 2 years (24-25).

Due to unsatisfactory results obtained with both conventional chemotherapy and SCT, it has become clear that new high-dose intense chemotherapeutic regimens are needed to improve the survival rates for patients with MCL. Similar intensity protocols have been used for treatment of Burkitt's lymphoma. Magrath treated patients with Burkitt's lymphoma using the CODOX-M protocol, which consisted of cyclophosphamide, doxorubicin, prednisone, vincristine, high-dose methotrexate and intrathecal methotrexate, alternating with IVAC (ifosfamide, etoposide, high-dose cytarabine and intrathecal methotrexate). This regimen resulted in excellent disease control and was

relatively well tolerated in both children and adults (17). Mead et al used this same regimen in 52 patients with Burkitt's lymphoma. All patients developed grade 3/4 neutropenia and 64% of the patients developed grade 3/4 thrombocytopenia. The only other significant side effect was mucositis, observed in about 40% of the cases (18). We have therefore developed a similar intense protocol combining most of the agents that demonstrated activity in MCL in an attempt to provide a better disease control with improved response rates and overall survival. Since a recent study has demonstrated a beneficial effect of thalidomide in patients with mantle cell lymphoma, patients were offered the option to receive maintenance thalidomide after the completion of the induction therapy as a consolidation to the aggressive chemotherapy (25a).

## 2.0 OBJECTIVES

### 2.1 Primary Objectives

To provide long-term follow-up and/or offer continued maintenance thalidomide (THALOMID®) to patients enrolled in 20030165.

### 2.2 Secondary Objectives

To continue to evaluate objectives specified for 20030165 (please refer to 20030165 for details).

## 3.0 ENDPOINTS

### 3.1 Primary endpoint

Progression-free survival (PFS): Patients will be evaluated at least annually and at the discretion of the treating Investigator. PFS is defined as the time from 20030165 enrollment until documented disease progression or death (by any cause, in the absence of progression). In progression-free patients, PFS will be censored at the last evaluable tumor assessment (clinical, hematologic, and/or radiographic).

#### 3.1.1 Criteria for Evaluation

- Evaluable for PFS: Any eligible subject enrolled into the SCCC 20030165 study, who received protocol-specified therapy.

### 3.2 Secondary endpoints

Progression-free survival (PFS): Patients will be evaluated at least annually and at the discretion of the treating Investigator. PFS is defined as the time from 20030165 enrollment until documented disease progression or death (by any cause, in the absence of progression). In progression-free patients, PFS will be censored at the last evaluable tumor assessment (clinical, hematologic, and radiographic).

Overall survival (OS): Patients will be evaluated at least annually. OS is defined as the elapsed time from 20030165 enrollment to death or date of censoring. Patients alive or lost to follow-up will be censored at the last date of contact (or last date known to be alive).

Response rate (RR): Patients will be evaluated at least annually or more frequently as clinically indicated and at the Investigator's discretion. Response rate is defined as the percentage of patients whose cancer shrinks or disappears after treatment.

Toxicity: Monitoring of AEs including serious adverse events (SAEs). AEs will be assessed in terms of nature, grade and attribution to treatment, using the National Cancer Institute Common Terminology Criteria for Adverse Events (NCI CTCAE), Version 3.0. Patients on maintenance thalidomide (THALOMID®) will be evaluated for adverse events (AEs) continually while on study.

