### 12.2 Evaluations on Treatment for Group A

The following evaluations should be performed as described. Additional tests are at the discretion of the Investigator.

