#### 12.2.2 Annually (every 12 months, ±30 days)

- Physical exam (PE)
- Complete Blood Count (CBC), including
  - Differential (diff) and
  - Platelet count (PLT)
- Comprehensive Metabolic Panel (CMP)
- Lactate dehydrogenase (LDH)

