#### 12.3.1 Annually (every 12 months, ±30 days)

- Physical exam (PE)
- Complete Blood Count (CBC)
  - Differential (diff) and
  - Platelet count (PLT)
- Comprehensive Metabolic Panel (CMP)
- Lactate dehydrogenase (LDH)

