#### 12.5 Off-Treatment Evaluations (End of Treatment or EOT) for Group A

The following assessments should be performed at the EOT visit and should occur 30-days (± 5 days) after the last dose of thalidomide.

- Physical exam (PE)
- Complete Blood Count (CBC), including
  - Differential (diff) and
  - Platelet count (PLT)

- Comprehensive Metabolic Panel (CMP)
- Lactate dehydrogenase (LDH)
- **(Additional for WoCBP)** Serum pregnancy test: (beta-HCG)

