## 12.7 Calendar of Clinical and Laboratory Evaluations

|   | Baseline | Every 4 weeks
(±5 days) | Every 12 months
(±30 days) | Off-Treatment A | Follow-up B |  |  |  |  |  |
|---|----------|----------------------------|-------------------------------|----------------------------|------------------------|--|--|--|--|--|
| (Group A)
thalidomide
(THALOMID®)  |          | Once daily A    |                               |                            |                        |  |  |  |  |  |
| Informed consent  | X        |                            |                               |                            |                        |  |  |  |  |  |
| Eligibility   | X        |                            |                               |                            |                        |  |  |  |  |  |
| Physical exam   |          |                            | X                             | X                          |                        |  |  |  |  |  |
| CBC w/diff, plts  |          |                            | X                             | X                          |                        |  |  |  |  |  |
| CMP   |          |                            | X                             | X                          |                        |  |  |  |  |  |
| Lactate dehydrogenase (LDH)   |          |                            | X                             | X                          |                        |  |  |  |  |  |
| Beta-HCG (WoCBP)  |          | X A             | X A                | X                          |                        |  |  |  |  |  |
| Adverse event evaluation  |          | X A             |                               |                            |                        |  |  |  |  |  |
| Survival  |          |                            |                               |                            | X B         |  |  |  |  |  |
| Footnote(s):   |          |                            |                               |                            |                        |  |  |  |  |  |
| A To be done only for patients in Group A                                      |          |                            |                               |                            |                        |  |  |  |  |  |

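### Does listing PFS as both primary and secondary endpoint, with "and/or" in one censoring rule and "and" in the other, change the PFS result?

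*Protocol*

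**What the plan says.** Section 3.1 names PFS as the primary endpoint, measured from enrollment in 20030165 to progression or death. For patients without progression it states: "PFS will be censored at the last evaluable tumor assessment (clinical, hematologic, and/or radiographic".

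Section 3.2 opens the secondary endpoints with PFS again. The visit frequency and definition are repeated, but the censoring sentence now reads: "PFS will be censored at the last evaluable tumor assessment (clinical, hematologic, and radiographic".

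The evaluable set in 3.1.1 is "Evaluable for PFS: Any eligible subject enrolled into the SCCC 20030165 study, who received protocol-specified therapy", and 3.2.1 repeats it.

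The annual visits in 12.2.2 (Group A) and 12.3.1 (Group B) consist of physical exam, blood count, "Comprehensive Metabolic Panel (CMP") and "Lactate dehydrogenase (LDH"). The Group A end-of-treatment visit in 12.5 has the same items, plus a pregnancy test where applicable. The calendar in 12.7 has no imaging row. Sections 12.2 and 12.3 both add: "Additional tests are at the discretion of the Investigator".

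**The concern.** An endpoint normally has one rank and one definition. Here PFS has two ranks, and the only difference between the entries lies in the rule that sets the censoring date. Under and/or, a physical exam with a blood count is enough. Under a strict reading of and, an assessment would count only if it also included imaging, which Section 12 never schedules.

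Event-free patients would then be censored at their last discretionary or standard-of-care scan, possibly one from 20030165. Progressions and deaths would still count at their own dates. Removing event-free time while keeping events shrinks the risk sets ahead of later events and pulls the Kaplan-Meier curve down. Two analysts working from the two sections could report different PFS curves.

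**Working it through.** The protocol states no alpha, power or event target, and none bears on this point. The check is a comparison of texts and a count.

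**1. The two entries side by side**

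| Element | 3.1 / 3.1.1 | 3.2 / 3.2.1 |
|---|---|---|
| Time origin | Enrollment in 20030165 | Same |
| Events | Progression, or death from any cause | Same |
| Evaluable set | Eligible and treated in 20030165 | Same |
| Censoring modalities | Clinical, hematologic, and/or radiographic | Clinical, hematologic, and radiographic |

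One word separates them.

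**2. Scheduled visits that can supply a censoring date.** There are six post-baseline visit types: Group A monthly, Group A annual, Group B annual, Group C annual, Group A end of treatment, and follow-up of all patients.

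- Under and/or: Group A annual, Group B annual and Group A end of treatment qualify, 3 of 6.
- Under an all-three reading: 0 of 6.

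**3. Which reading the protocol supports.** The parenthesis follows a single assessment and names the types that may make it up. Read as a list, it gives the 3.1 rule. Section 13.5 says that follow-up at least annually documents the progression-free interval, and the annual visits contain no imaging, so the all-three reading would defeat 13.5. Section 3.1 itself says and/or. Nothing in the protocol requires all three.

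**4. Imaging outside the calendar.** Section 13.0 has response evaluated under standard of care until progression, and the criteria in 13.2 rely on radiographic evidence and nodal measurements. Sections 12.2, 12.3 and 13.5 allow further tests at discretion. Even under the strict reading, qualifying assessments could therefore occur, though not at fixed times.

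**5. Who could be affected.** From the Synopsis, Groups A and B have 2 + 12 = 14 patients; with Group C the total is 14 + 8 = 22, and 14/22 = 64%. Group C is defined by death or progression, so its patients already have PFS events. The 14 are an upper limit, since any of them who later progress or die leave the censored set.

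**6. Size under the unlikely reading.** A later event with n patients at risk multiplies the Kaplan-Meier estimate by (n − 1)/n. Assume one later event. With all 14 still at risk the factor is 13/14 = 0.93. If every other patient has already been censored it is (1 − 1)/1 = 0. With no event after the earlier censoring dates, that reading leaves the estimate unchanged beyond those dates. The protocol gives neither rollover times, nor scan dates, nor the number of later events, so no value in this range can be preferred. Under the list reading the effect is exactly zero.

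**The case for a change.** The best case for acting is that this is not a detail left for an analysis plan to fill. The protocol fixes the endpoint twice in different words, and whoever writes the analysis must choose. PFS is the named primary endpoint, Section 7.0 speaks of including Group C in all analyses, and Section 15.0 leaves open merging the results with 20030165. Deleting the second entry costs nothing.

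The duplication and the difference in wording stand. The consequence does not. The choice is already made: the primary endpoint follows 3.1, which is also the rule an editorial correction would keep. Section 15.0 plans no formal analysis, and no error rate, testing order or success criterion attaches to primary or secondary status. The secondary objective in 2.2 refers back to 20030165, so the second listing may have been carried over from there; that cannot be checked from this protocol.

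One may also say that and/or is loose, since a blood count alone could pass as a disease assessment. That belongs to 3.1 and would remain after the duplicate was removed.

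**Conclusion.** The concern is right on the text but does not call for a change. PFS appears twice through a drafting slip, and the single differing word leaves the rule intact when the parenthesis is read as a list of modalities, as 3.1 and 13.5 indicate. Under that reading the effect on PFS is nil. Under the all-three reading at most 14 of 22 patients could have an earlier censoring date, and the size of any bias cannot be determined from the protocol. The conclusion rests on two points: that 3.1 governs the primary endpoint, and that no decision depends on the second listing. Section 15.0 supports the second. Removing the duplicate would be tidier, but no result would differ.

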### 3.2.1 Criteria for Evaluation

- Evaluable for PFS: Any eligible subject enrolled into the SCCC 20030165 study, who received protocol-specified therapy.
- Evaluable for OS: Any eligible subject enrolled into the SCCC 20030165 study, who received protocol-specified therapy.
- Evaluable for RR: Eligible patients enrolled into the SCCC 20030165 study, who receive protocol-specified therapy.
- Evaluable for Toxicity: Eligible patients in Group A, enrolled into the SCCC 20030165 study, who experience AEs while receiving thalidomide (THALOMID®).

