## 7.0 STUDY DESIGN

The study is designed to provide long-term follow-up, as well as to offer continued thalidomide (THALOMID®) maintenance therapy to patients enrolled in 20030165.

There are 14 eligible patients in Groups A and B expected to rollover from 20030165. An additional Group C consisting of all other patients who expired or experienced disease progression on 20030165, will also be included in all analyses.

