#### 9.1.4 Management of Agent-Specific Adverse Events

Most patients taking thalidomide can be expected to experience adverse reactions.

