#### 12.2.1 Monthly (every 4 weeks, ±5 days)

- **Additional for Women of Childbearing Potential (WoCBP) receiving thalidomide maintenance therapy (Group A):** Serum pregnancy test: (beta-HCG)
- Adverse Events (AEs): Monitoring and collection of Adverse Events (AEs) should occur throughout the study for patients in Group A.

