### 15.0 STATISTICAL CONSIDERATIONS

At this time, no formal statistical analysis is planned for this long-term follow-up study. If necessary, and as deemed by the Principal Investigator (PI), the results of this trial will be integrated with the 20030165 trial analyses.

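### Section 3.2.1 makes having an adverse event a condition of being evaluable for toxicity, so treated Group A patients without one drop out of the denominator

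*Protocol*

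**What the plan says.** Section 3.2.1 lists who is evaluable for each secondary endpoint. For toxicity the entry reads "Evaluable for Toxicity: Eligible patients in Group A, enrolled into the SCCC 20030165 study, who experience AEs while receiving thalidomide (THALOMID").

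The other entries are built differently. For survival: "Evaluable for OS: Any eligible subject enrolled into the SCCC 20030165 study, who received protocol-specified therapy". For response: "Evaluable for RR: Eligible patients enrolled into the SCCC 20030165 study, who receive protocol-specified therapy". The PFS entries in Sections 3.1.1 and 3.2.1 follow the same pattern.

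On who is observed for AEs, Section 3.2 states "Patients on maintenance thalidomide (THALOMID®) will be evaluated for adverse events (AEs) continually while on study", and Section 12.2.1 states "Monitoring and collection of Adverse Events (AEs) should occur throughout the study for patients in Group A". Neither sentence requires that an AE has already occurred. No other section of the protocol gives a different toxicity set.

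The Synopsis expects 2 patients in Group A. Section 15.0 states "At this time, no formal statistical analysis is planned for this long-term follow-up study", but leaves open that results may be combined with the analyses of trial 20030165 if the principal investigator sees a need.

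**The concern.** A set used to describe how often something happens should be fixed by exposure, not by whether it happened. Here the only exposed patients who count are those with an event. A treated patient who was monitored and stayed free of AEs is favourable safety information, and the definition discards it.

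Two things follow for any per-patient summary on this set. The proportion with at least one AE carries no information, because it cannot take any value other than 100%. Proportions by type, grade or attribution, which are the features Section 3.2 names for assessing AEs, are overstated whenever that AE occurs in one patient and another treated patient is AE-free. The error would matter if AE frequencies were reported from this study or carried into the 20030165 analyses.

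**Working it through.** The protocol gives no toxicity rate or sample-size figure for this endpoint, so there is no figure of its own to reproduce. The check compares the two denominators.

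**Inputs**
- Expected Group A size: n = 2 (Synopsis). This agrees with Section 7.0, "There are 14 eligible patients in Groups A and B expected to rollover from 20030165", since 2 + 12 = 14.
- Probability p that a patient has a recorded AE: not given for this population, so a range is assumed. Section 9.1.4 says only "Most patients taking thalidomide can be expected to experience adverse reactions".
- The two patients are assumed independent.

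**Proportion with any AE, by number of patients affected (x)**

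| x | Set as written (x/x) | All treated Group A (x/2) | Exact 95% interval for x/2 |
|---|---|---|---|
| 0 | 0/0, undefined | 0/2 = 0% | 0% to 84% |
| 1 | 1/1 = 100% | 1/2 = 50% | 1.3% to 98.7% |
| 2 | 2/2 = 100% | 2/2 = 100% | 16% to 100% |

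For x = 1 the Clopper-Pearson limits are 1 − √0.975 = 0.0126 and √0.975 = 0.9874.

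**Proportion with a specific AE or grade.** If k of n treated patients have it and m treated patients have no AE at all, the set as written gives k/(n − m) instead of k/n, an inflation factor of n/(n − m) when k > 0. With n = 2, m = 1, k = 1 this is 1/1 instead of 1/2, a factor of 2.

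**How likely the two denominators are to differ**
- False 100% (exactly one patient affected): 2p(1 − p)
- 0/0 (none affected): (1 − p)²
- No error (both affected): p²

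| Assumed p | False 100% | 0/0 | No error |
|---|---|---|---|
| 0.5 | 0.50 | 0.25 | 0.25 |
| 0.8 | 0.32 | 0.04 | 0.64 |
| 0.9 | 0.18 | 0.01 | 0.81 |

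Each row sums to 1. At higher p the chance of any difference, 1 − p², falls further: 0.10 at p = 0.95 and 0.02 at p = 0.99.

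**The case against.** The strongest reply is that nothing planned uses this set as a denominator. Section 3.2 defines response as a percentage of patients but describes toxicity only as monitoring and characterising events, and Section 15.0 plans no formal analysis. On that view the entry merely says whose events will be described, and an AE-free patient has no event to grade or attribute. Safety oversight is also untouched: targeted collection (Section 14.5), AE recording (Section 14.7), expedited reporting (Appendix A) and data and safety monitoring committee review (Section 16.1) do not refer to this set, so no event is lost.

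This stands as a limit on importance. It does not rescue the wording. The list in Section 3.2.1 defines evaluable patients, not events, and a patient whom the protocol evaluates for AEs throughout cannot sensibly be called not evaluable for them. Nor is this a detail left to an SAP (none was available for this review): the protocol states a rule, and the rule is wrong.

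A second reply is that nearly everyone will have an AE. Table 2 in Section 9.1.4 reports at least one adverse reaction in 233 of 234 patients on thalidomide with dexamethasone. At that p the denominators would differ with probability 1 − (233/234)² ≈ 0.9%. That figure comes from combination treatment in myeloma. The targeted collection in Section 14.5 is confined to serious, potentially serious, treatment-stopping and unexpected related events, which could lower the number of patients with a recorded AE here. It is therefore a favourable extreme and not a forecast.

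A third reply is that limiting the corrected set to thalidomide taken on this study adds a scope choice, since Group A patients continue treatment begun under 20030165. The limit is consistent with Section 3.2, which evaluates these patients while on study, and with Section 14.4, which counts only events that begin or worsen after protocol treatment starts. The essential correction is to remove the outcome condition.

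**Conclusion.** The concern holds. The toxicity set in Section 3.2.1 is wrong as written: it selects on the outcome, departs from every other evaluable set in the protocol, and is at odds with the AE monitoring in Sections 3.2 and 12.2.1. Any overall AE proportion computed on it is 100% or undefined.

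The severity is minor. The endpoint is secondary, two patients are expected, no rate is named, and there is no error at all if both patients have an AE. The false-100% result depends on exactly one of the two being affected; its probability (0.18 to 0.50 over p from 0.9 to 0.5) rests on an assumed p and on independence. Even the correct 1/2 has an interval covering almost the whole range, so what is gained is a valid rule and not useful precision. The conclusion about the rule needs none of these assumptions.

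**What to change.** Replace the toxicity entry in Section 3.2.1 with: *Evaluable for Toxicity: all eligible Group A patients who receive at least one dose of thalidomide on this study, whether or not they experience an AE.* Use that set as the denominator for any AE summary, including any that is combined with the 20030165 results.

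The cost is one sentence. No further data collection is needed: AE monitoring (Section 12.2.1), the monthly drug-dispensing record (Section 17.5) and the Group A Treatment Form (Appendix B) already cover these patients. With two patients expected, reporting counts as x of n alongside a patient listing is sufficient.
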